9.3.3. Exploratory Hypothesis

There are no exploratory hypotheses.

9.4. Sample Size Determination

The following evidence was used to support the sample size calculation of the first primary endpoint:

Cochlear[™]'s feasibility clinical investigation CLTD5495 comparing outcomes of the dexamethasone eluting Cl400 Combined Investigational Device (Cl4CID) and standard Cl24RE(CA) device. At 6 months post-activation MP1+2 impedance data showed a decrease of 3.8 kOhms for the Cl4CID compared to the Cl24RE(CA). The Cl4CID standard deviation from its mean was 1.0 while the Cl24RE(CA) standard deviation was 1.7. The electrode array used in this clinical investigation is the Contour Advance electrode.

CI632 predicate device is the Cochlear[™] Nucleus[®] CI532 cochlear implant with Slim Modiolar electrode (CI532). Six month mean MP1+2 impedance data for 43 subjects under the clinical investigation CLTD5446 provides similar results to the CI24RE(CA) control group of the CLTD5495 clinical investigation, with mean MP1+2 impedance measuring at 7.9 kOhms with a standard deviation of 1.7.

Considering results from CLTD5495 and CLTD5446, the following assumptions have been made regarding this clinical investigation:

Using an independent t-test (SigmaPlot 13.0) the sample size has been calculated to have reasonable power to detect a 1.5 kOhm decrease difference in MP1+2 impedance at 6 months post-cochlear implant for those implanted with the CI632D IMD compared to those implanted with the CI632 comparator device.

This change of 1.5 kOhms to be detected is based on clinical consensus and has taken into consideration the significant mean impedance reduction (3.8 kOhms) observed in the CI4CID feasibility clinical investigation CLTD5495. Due to the nature behind the design of CI632, it is likely there will be less insertion trauma as it is a precurved electrode designed to stay closer to the medial wall of the cochlea.

An expected standard deviation (SD) of the change is 2.0 kOhms. This SD of the change to be detected is based on the SD of the mean impedance of 1.7 observed in separate clinical investigations for CI24RE(CA) and CI532. The expected standard deviation of the mean in the current study has been chosen to be more conservative, allowing for increased impedance variability between the two arms.

A significance level α = 0.025 (one-tailed).

A desired power of 0.9

The sample size for a 1:1 allocation has been calculated to have reasonable power to detect a decrease in mean (SD) MP1+2 impedance of 1.5 kOhm (1.5) for the CI632D IMD compared to the CI632 comparator device at 6 months post-implantation.

A 1.5 kOhms drop in impedance is expected to result in a mean increase in battery life of 1.79 hours for recipients with high powered maps, demonstrating a meaningful clinical benefit. This calculation is based on prior investigation using the DEE battery model (D1672865).

In the absence of literature to support a clinically meaningful change in impedance values for cochlear implants, the Sponsor positions 1.5kOhms effect size as clinically meaningful as shown by the battery life model increasing battery life by a mean of 1.79 hours. An improvement of 1.79 hours in battery life clearly equates to a meaningful duration of time for a cochlear implant recipient, such as a round trip commute to work, multiple meetings at work, a child's soccer game, meal out with friends, etc. The clinical investigation is powered to capture the 1.5kOhm effect size.

Based on these assumptions, a minimum sample size of 39 subjects in both arms is required to reject the null hypothesis of equivalent or higher MP1+2 impedance for the Cl632D IMD compared to the Cl632 comparator device at 6 months post-implantation with a power > 0.9. An increased sample size of 100 subjects (approximately 50 subjects in each arm) will be included, which will allow for the possibility of non-normally distributed data (approximately 15%) and subject attrition (approximately 10%). In addition, the population is extended to 120 randomised subjects to account for uncertainty in the estimates used in the power calculation, with approximately 60 subjects in each arm.

The following evidence and assumpters were used to support the same size calculation of the second primary endpoint:

CI632 predicate device is the Cochlear[™] Nucleus[®] CI532 cochlear implant with Slim Modiolar electrode (CI532). Six month mean CNC word in quiet data 96 subjects under the clinical investigation CLTD5685 provided a mean change of 46 ± 22.6 (SD) word improvement from baseline

A significance α = 0.025 (one-tailed).

A desired power of 0.9

A 10% improvement at 6 Months post-cochlear implant is required to reject the null hypothesis. Based on these assumptions, a minimum sample size of 10 subjects is required to reject the null hypothesis of equivalent or lower CNC words in quiet for the Cl632D at six month post-cochlear implant compared to baseline with a power > 0.9. To account for non-normally distributed data (approximately 15%) and subject attrition (approximately 10%), not less than 13 subjects need to be randomised to Cl632D ("treatment"

group) and successfully implanted. More than 13 subjects will be randomised to the treatment to meet sample size requirements for the first primary endpoint.

As the CI632D is a novel medical device, a group sequential analysis strategy is planned. The first analysis will occur with the first 50 randomised subjects completing the 6 month endpoint. If stopping criteria are not met, the analysis will be repeated at 80 subjects, 100 subjects and 120 subjects.

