7.2.1 Inclusion Criteria

Subjects must meet all of the inclusion criteria described below to be eligible for this clinical investigation.

- 1. Postlingual, bilateral, moderate to profound sensorineural hearing loss, defined by a pure-tone average (PTA):
 - a. \geq 40 dB HL at 250 through 1000 Hz and,
 - b. \geq 65 dB HL at 2000 through 8000 Hz.
- 2. Preoperative aided word score is 40% correct or less in the ear to be implanted (60% or less in the contralateral ear).
- 3. 18 years or older at time of consent.
- 4. Willing to be randomised into either a treatment (CI632D) or control (CI632) arm.
- 5. Evidence of pneumococcal vaccination (e.g. Pneumovax) according to local guidelines prior to randomisation.
- 6. Fluent speaker in the local language used to assess clinical performance as judged by the investigator.
- 7. Willing and able to provide written informed consent.

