9.3.1.2. Primary Endpoint #2

Mean CNC word score in quiet will show at least 10% improvement with the Cl632D ("treatment" arm) at 6 months post-implant compared to "treatment" arm's preoperative Baseline, is as follows:

H0: CI632D CNC word_{6 Month} < CI632D CNC word_{Baseline} + 10%

H1: CI632D CNC word_{6 Month} \geq CI632D CNC word_{Baseline} +10%

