9.6. Endpoint Analyses

9.6.1. Primary Endpoint Analyses

There are two primary endpoints.

Primary analysis of MP1+2 impedances will include the ITT population evaluating mean differences at 6 months post-cochlear implantation based on a t-test at the one-sided 0.025 alpha level. If there is evidence of non-normality (based on a Shapiro-Wilks test at the 0.05 alpha level), a non-parametric alternative will be employed for the primary endpoint.

Primary analysis of speech perception performance will include the cohort of subjects randomised to CI632D and for whom CI632D is their first cochlear implant in the ITT population, evaluating the difference at 6 months post-cochlear implantation compared to baseline via a one-sample sample t-test at the one-sided 0.025 alpha level. If there is evidence of non-normality (based on a Shapiro-Wilks test at the 0.05 alpha level), a non-parametric alternative will be employed for the primary endpoint.

For both endpoints, analysis may include description of population differences in the final analysis. Additional analysis may include both the AS and PP analyses groups. Missing data will be analysed under a multiple imputation strategy that will be outlined in the Statistical Analysis Plan (SAP).

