9.8. Interim Analyses

Group sequential analysis based on an O'Brien-Fleming like alpha spending function, will be completed for the primary endpoints following the collection of 6 Month data for subjects at the following intervals: the first 50 randomised subjects, first 80 randomised subjects, first 100 randomised subjects, and first 120 randomised subjects. If the null hypothesis cannot be rejected for both primary endpoints following analysis at each interval (stopping criteria), then further analysis will take place at the subsequent interval until the final analysis of the 120 randomised subjects.

The first primary endpoint will be analysed first. The second primary endpoint will be analysed if the null hypothesis is rejected. Analysis of secondary or exploratory endpoints will not occur until both the primary endpoint null hypotheses are rejected, or 120 randomised subjects are analysed.

Prior to final analysis at study completion, group sequential analysis may be used as part of Premarket Approval (PMA) if both primary endpoint null hypotheses are rejected.

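### The protocol states the null hypothesis of primary endpoint 2 inconsistently (a 10% gain in Section 9.3.1.2, zero gain in one sentence of Section 9.4), and the stated minimum of 10 does not follow from the planned one-sample test under either

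*Protocol*

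**What the plan says.** Section 9.3.1.2 gives the hypothesis in words, "Mean CNC word score in quiet will show at least 10% improvement", and in symbols: the null is a 6-month score below baseline plus 10%.

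Section 9.4 takes its planning figures from an earlier study of the predicate device, which "provided a mean change of 46 ± 22.6 (SD) word improvement from baseline", with one-sided alpha 0.025 and a desired power of 0.9. It then says "A 10% improvement at 6 Months post-cochlear implant is required to reject the null hypothesis". The sentence after that says "a minimum sample size of 10 subjects is required to reject the null hypothesis of equivalent or lower CNC words in quiet" for the CI632D at six months compared with baseline. The minimum of 10 is raised to 13 for non-normality (about 15%) and attrition (about 10%).

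Section 9.6.1 describes the analysis as the 6-month difference "compared to baseline via a one-sample sample t-test at the one-sided 0.025 alpha level". It does not mention the 10%.

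Section 9.8 puts this endpoint second in sequence: "The second primary endpoint will be analysed if the null hypothesis is rejected", meaning the null of endpoint 1. Rejecting both nulls is the stopping criterion and the condition for using an interim result in a premarket application.

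**The concern.** A score equivalent to or lower than baseline is a gain of zero or less. That is a different null from a gain of less than 10%, so two consecutive sentences of Section 9.4 describe different tests. The odd phrase closely follows the endpoint 1 wording in the same section, "required to reject the null hypothesis of equivalent or higher MP1+2 impedance", where a zero null is correct. It was probably carried over.

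The null value is the success threshold of a primary endpoint in a pivotal trial. Section 9.6.1 does not settle which value applies, because a one-sample test against baseline with no stated reference value is most simply read as a test against zero. A test against zero could support a claim of at least 10% improvement on an observed mean gain below 10 points. The sample size of 10 ought to show which null was used, but it does not match the named test under either one.

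**Working it through.** **Inputs.** Mean gain 46, SD 22.6, one-sided alpha 0.025 and power 0.9 (Section 9.4); one-sample t-test (Section 9.6.1); null at +10% (Section 9.3.1.2) or zero (the Section 9.4 sentence). I assume that the 46 and the 10% are on the same percentage-point scale.

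**Formulae.** Power is P(T > t(1−α, df)), where T is noncentral t. One-sample: df = n−1, noncentrality (d/SD)·√n. Two-sample with n per group: df = 2n−2, noncentrality (d/SD)·√(n/2). Here d is the planned gain minus the null value.

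**Reproducing the stated 10.** With d = 46−10 = 36, the two-sample formula gives power 0.887 at 9 per group and 0.920 at 10 per group. That matches the protocol's figure. The inflation also matches: 10 × 1.15 / 0.9 = 12.8, rounded up to 13.

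**Minimum n under each null.**

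| Null | d | One-sample n (power) | Two-sample n per group (power) |
|---|---|---|---|
| Zero gain | 46 | 5 (0.917) | 7 (0.937) |
| +10% relative, baseline 40% | 42 | 6 (0.948) | 8 (0.932) |
| +10 points absolute | 36 | 7 (0.936) | 10 (0.920) |

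The relative row uses the eligibility ceiling, "Preoperative aided word score is 40% correct or less in the ear to be implanted": 10% of 40 is 4 points, so d is at least 46−4 = 42. At lower baselines it approaches the zero-gain row. For the named test, n = 6 against +10 gives 0.872, so 7 is the minimum. At n = 10 its power is 0.994. Seven inflated the same way is 7 × 1.15 / 0.9 = 8.9, or about 9.

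**Observed gain needed to reject.** Assumptions: 25, 40, 50 and 60 treated subjects at the four looks (half of 50, 80, 100 and 120) with no attrition; SD 22.6; and spending 2·(1−Φ(z(0.9875)/√t)) as the O'Brien-Fleming-like function. The nominal alphas are about 0.0005, 0.006, 0.012 and 0.020. The threshold is the null value plus t(1−α_k, n−1)·22.6/√n:

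- against zero: 16.9, 9.4, 7.4 and 6.1 points;
- against +10: 26.9, 19.4, 17.4 and 16.1 points.

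Under the zero null, looks 2 to 4 could succeed on an observed gain below 10. Under the +10 null, an observed gain of exactly 10 never suffices, so the Section 9.4 sentence requiring a 10% improvement is not itself a rejection rule.

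**At the planned gain.** With d = 36, n = 25 and the first-look alpha of 0.0005, power against +10 is 0.9999.

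**Related slip in the same section.** For endpoint 1, Section 9.4 gives an expected SD of 2.0 kOhm and then restates the effect as 1.5 kOhm with 1.5 in brackets as the SD. With d = 1.5 and a two-sample t-test, SD 2.0 gives 39 per arm (power 0.905; 38 gives 0.897), which is the stated figure. SD 1.5 gives 23 (0.912).

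**The case against.** The best reply is that the test is already fixed. Section 9.3.1.2, the hypotheses section, gives the null in symbols with the 10%, and the sentence before the disputed one in Section 9.4 agrees. What remains is one loose clause in a sample-size paragraph, and a statistical analysis plan that is not shown here would normally carry the reference value. This largely stands. It is why the point is minor, and why the missing value in Section 9.6.1 is not a separate error. It does not remove the contradiction, which lies within the protocol.

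Two stronger readings are tempting, and neither is supported.

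- A reader might infer that the 10 subjects prove a +10-point null. They do not. The match needs a two-sample formula that the protocol never states for this endpoint, and other unstated settings also give 10: a zero-gain null with the two-sample formula reaches power 0.990 at 10 per group. At the stated power of 0.9 the +10 reading fits best, but it remains an inference.
- A reader might infer a badly inflated error rate. In simulation, with endpoint 1 at its planned effect (1.5 kOhm, SD 2.0) and independent of endpoint 2, a true gain of exactly 10 points is eventually declared a success about 90% of the time against zero and 2.4% against +10. That contrast requires an analyst to override the formal null and a true gain far below the planned 46. The documents make neither likely.

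**Conclusion.** The inconsistency is real and the correction is minor. Section 9.3.1.2 and one sentence of Section 9.4 require a 10% gain, the next sentence of Section 9.4 names zero gain, and Section 9.6.1 leaves the reference value unstated. The minimum of 10 is larger than the planned test needs under either null, so it is conservative and endpoint 2 is not under-powered. Enrolment is set by endpoint 1 in any case. The choice of null would change a decision only if the Section 9.4 or 9.6.1 wording were followed over the formal hypothesis and the true gain were near or below 10 points. These conclusions rest on the planning SD of 22.6 and on reading 10% as absolute points, which the protocol does not say.

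**What to change.** - Section 9.4: replace the zero-gain description of the endpoint 2 null with the null of Section 9.3.1.2. Reword the sentence on a 10% improvement so that it is not read as a rule about the observed mean.
- Section 9.3.1.2: state that 10% means absolute percentage points, if that is what is intended.
- Section 9.6.1: name 10 as the reference value of the one-sample test.
- Section 9.4: restate the endpoint 2 minimum as 7 (about 9 after inflation), or keep 10 and 13 and label them conservative.
- Section 9.4, endpoint 1: reconcile the bracketed 1.5 with the SD of 2.0 that gives 39 per arm.

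The cost is wording in three sections. Total sample size, looks and alpha are unchanged.

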9.5. Analysis Populations

Analyses of endpoints will include the following populations:

- Intent-to-Treat (ITT): all subjects that are randomised. Analysis will be based on randomisation assignment.
- As-Treated (AT): subjects that receive a CI632 or CI632D. Analysis will be based on treatment received (rather than randomisation assignment).
- Per-protocol (PP): subjects that receive a CI632 or CI632D in accordance with randomisation assignment and do not have a translocated electrode as confirmed by imaging.

In addition to these populations, there may be subgroup analysis which could include geography, sex, age or race. The complete analysis strategy will be outlined in the Statistical Analysis Plan (SAP).

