7.2.5 Recruitment and Study Duration

The following subject status definitions apply:

- Enrolled: A subject that has a signed the Informed Consent form for the study.
- Screen Fail: An Enrolled subject that has been determined to not meet one or more eligibility criteria.
- Participated: Consented subjects who have met all eligibility criteria, have qualified for surgery, and have been randomised.
- Implanted: A participating subject who has received the IMD/comparator in accordance to the randomisation assignment
- Treatment Failure: A participating subject who has not been successfully implanted or does not receive the IMD or comparator treatment in accordance with the randomisation assignment
- Discontinued: An Enrolled subject who withdrew consent, was discontinued by the Investigator or Sponsor before the expected End of Study visit or lost to follow-up. Discontinued subjects may still have safety follow up data collection until their scheduled End of Study visit, for reasons described in section 7.2.6.
- Completed: Enrolled subjects who complete the required treatment and visit schedule.

The recruitment period for the clinical investigation is estimated to be 28 months from the time of first subject consent to recruitment of the last subject. If the recruitment numbers increase following the interim analysis, the recruitment period is expected to extend approximately one month for every eight enrolments.

The expected duration of each subject's participation in the clinical investigation, is 14 months. From the time of implant through to the End-of-Study visit is 12 months after implantation.

Therefore, the anticipated total duration of the clinical investigation is 42 months. Clinical Investigation completion is at the last subject's last visit. In the event of ongoing SAEs/SADEs at the time of a subject's last visit, the subject's clinical investigation completion will be extended for a further 30 days, or until resolution or stabilisation of the event, whichever comes first.

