7.3.2.7.2. Randomisation

Randomisation may only be completed once all activities under Screening and Baseline are completed, subject screening/baseline data is entered into the EDC, and eligibility has been confirmed by an independent Sponsor representative.

The ear to be implanted will need to be determined prior to randomization and must be compliant with the inclusion and exclusion criteria. The decision will be made between the investigator, audiologist and subject, and the justification for ear selection must be documented.

7.3.2.7.3. Surgery (day 0)

Data collection from time of Surgery through discharge from hospital includes:

• High Resolution CT: Post insertion to assess electrode placement. Cone beam CT and flat panel CT are examples.

OR

- X-Ray or fluoroscopy (C-arm): required intraoperatively to assess placement of electrode using Modified Stenver's View. X-ray or fluorscopy will be repeated if electrode is repositioned/replaced.
 - If final placement of cochlear implant is not positioned correctly (tip foldover or translocation), the subject will remain in the clinical investigation and complete all assessments. Outcome will be documented in the CRF.
- Electrode Electrical Testing: must be completed intraoperatively after final placement of electrode. If electrode position is altered or second device is used, testing must be repeated. Complete tests in the following order:
 - 1. Impedances (MP1+2 and Four point).
 - 2. AutoNRT[®] (standard 9 electrodes).
- Surgical Questionnaire: surgeon's review of surgical implant.
- Discharge Summary: subject's stay in hospital.

The following requirements are to be followed for the Surgery:

- At the surgeon's discretion, dexamethasone may be utilised in anaesthesia, IV and take-home pack, which will be documented in the CRF.
- Dexamethasone may not be used to treat (e.g. topically) the cochlear implant electrode.
- Dexamethasone may not be used within or near the ear/cochlea.
- Cochlear implant electrode may not be dipped in saline, hyaluronic acid (healon), or other treatment prior to insertion.
- The implant procedure must follow Instructions for Use (IFU). A back up CI632D or CI632 may be required if preparation/insertion is not possible according to IFU.
- Following impedance and/or NRT testing, if the electrode is re-inserted or replaced with a new device, the testing must be repeated

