If the IMD or comparator is inserted but not implanted (eg implanted with commercial device), the subject should remain in the clinical investigation for 30 Days or until all AEs are resolved (whichever is longer).

If the IMD or comparator is implanted and then explanted during Surgery or at a later date, the subject should remain in the clinical investigation for 30 Days or until all AEs are resolved (whichever is longer).

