9.7. Safety Analyses

Safety analysis will be completed with the AT population at both 6 months and 12 months post-cochlear implantation. The rate of AE type will be compared between treatment and control arm.

For AE/ADEs and DDs, data will be tabled to present event type, severity, device/procedural relationship, count and percentage, and subjects with event will be summarised by randomisation group. Any subjects who died, who discontinued an intervention due to an AE/ADEs, or who experienced a severe or an SAE/SADEs will be summarised separately. In addition to Secondary Endpoint Analyses, AE/ADE and DD frequency data will be provided to the IDMC in accordance to the IDMC Charter.

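### Safety is analysed only in subjects who receive a CI632 or CI632D, so a subject whose study array was inserted and abandoned for another implant falls outside the between-arm comparison, and sections 9.5 and 9.7 disagree on grouping

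*Protocol*

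**What the plan says.** - **Population (section 9.5).** The As-Treated (AT) population is "subjects that receive a CI632 or CI632D. Analysis will be based on treatment received". The other populations are intent-to-treat and per-protocol. There is no separate safety set.
- **Safety analysis (section 9.7).** "Safety analysis will be completed with the AT population at both 6 months and 12 months post-cochlear implantation". It adds: "The rate of AE type will be compared between treatment and control arm". The next paragraph, on the event tables, says that "subjects with event will be summarised by randomisation group".
- **Surgery (section 7.3.2.7.3).** The protocol foresees an abandoned array: "If the IMD or comparator is inserted but not implanted (eg implanted with commercial device), the subject should remain in the clinical investigation". This follow-up lasts at least 30 days, and longer if adverse events are unresolved. A separate paragraph covers a device that is implanted and then explanted, including during surgery. On spares: "A back up CI632D or CI632 may be required if preparation/insertion is not possible according to IFU".
- **Subject status (section 7.2.5).** An implanted subject is one who has received the device assigned at randomisation. A treatment failure is "A participating subject who has not been successfully implanted or does not receive the IMD or comparator treatment" as assigned.
- **Collection (section 11.2).** Adverse events are recorded from randomisation onwards.
- **Use (sections 6.2 and 9.2.2).** Secondary endpoint 1 compares procedure- and device-related adverse events between the two devices. It serves the objective of showing that their safety is similar.

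**The concern.** An abandoned insertion is a setting in which procedural events may plausibly arise: an array has entered the cochlea, has come out, and another may have gone in. The protocol foresees this case and collects its events, but then defines the safety population by receipt of a device rather than by attempted insertion. Whether such a subject counts is therefore settled by what happens during surgery, after randomisation, in the hands of a surgeon who knows the assignment (section 7.2.7.1).

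At stake is the between-arm safety comparison. It carries no formal hypothesis test (section 9.3.2), so the descriptive rates are themselves the evidence for similar safety. Their denominators and arm labels need to be right.

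**Working it through.** No figure in the protocol depends on this definition, so there is none to reproduce. The check sets the sections side by side and then sizes one subject.

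**Step 1: what receiving a device means.** Section 9.5 does not define the term. Section 7.2.5 uses it to define the implanted status and places a subject who was not successfully implanted among the treatment failures. Section 7.3.2.7.3 separates inserted from implanted. On this usage, an array that was only inserted was not received.

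**Step 2: follow one subject.** Take a subject randomised to CI632D whose array was inserted and abandoned.

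| Device finally in place | Section 9.5, by treatment received | Section 9.7, by randomisation group |
|---|---|---|
| A second CI632D | In AT, as CI632D | CI632D |
| Another commercial implant, or none | Not in AT | Names an arm, but does not bring the subject back into AT |
| A CI632 | In AT, as control | CI632D |

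The first row is sound. In the second, the events are collected but are missing from the AT comparison. The third row shows two grouping rules giving different arms for the same subject.

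**Step 3: size of one subject.** The arm size is at most 60 (section 7.1). One subject is 1/60 = 1.7 percentage points of an arm's event rate.

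The protocol gives no abandonment rate. *Assuming* 1% to 3%, the expected number per arm is 0.01 × 60 = 0.6 to 0.03 × 60 = 1.8.

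**Step 4: illustration with assumed counts.** Suppose that, with every attempted insertion kept in the arm of the array first inserted, the event rates are 6/60 = 10.0% for CI632D and 3/60 = 5.0% for CI632. Let *k* of the six CI632D events belong to subjects with abandoned insertions.

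| *k* | CI632D rate with those subjects dropped | CI632 rate |
|---|---|---|
| 1 | 5/59 = 8.5% | 5.0% |
| 2 | 4/58 = 6.9% | 5.0% |
| 3 | 3/57 = 5.3% | 5.0% |

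Here *k* = 2 lies just above the assumed range, and *k* = 3 would need 3/60 = 5% abandonment, all with events. If abandonment and its events were equally frequent in both arms, both rates would fall and the difference would move little.

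**The case against.** **The term is undefined, and the SAP may settle it.** The AT definition could be read to cover any insertion, and a device implanted and then explanted during surgery was arguably received. That is fair, and it is why the point rests on the narrower case of an array inserted but never implanted. There, the protocol's own usage in 7.2.5 and 7.3.2.7.3 points to exclusion. The population is also fixed in 9.5 and 9.7 rather than left open, so a SAP that included these subjects would be reinterpreting this text.

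**The events are not lost.** This stands. They are recorded from randomisation. Deaths, discontinuations for adverse events and serious events are summarised separately in a paragraph of 9.7 that does not repeat the AT restriction. The monitoring committee reviews serious device effects and infection-related events (section 8.4). The gap is confined to the between-arm comparison.

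**A reader might infer that abandoned CI632D insertions are counted as controls.** The text does not establish this. The sentence on spares is most naturally read as a spare of the assigned type. A commercial CI632 as replacement is only an inference from the statement in section 8.5 that the CI600 series is on the market. The randomisation-group sentence in 9.7 would also table the subject under CI632D. What stands is that 9.5 and 9.7 conflict if the case occurs.

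**A reader might also infer a bias towards similar safety.** That would need abandonment to be more frequent with CI632D, and nothing in the protocol says so. Section 5.2 describes the devices as identical apart from the drug wells, and section 8.4 says that technique and handling do not differ.

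**Conclusion.** The point holds in two parts. First, followed as written, the safety population leaves out a subject whose study array was inserted and then replaced by a device that is neither CI632 nor CI632D, although that subject's events are collected. Second, 9.5 and 9.7 give different grouping rules for the safety data, and the difference matters for any subject whose final device is not the assigned type.

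Each affected subject is worth about 1.7 percentage points with 60 per arm, and more in smaller arms. The number affected is unknown; the 0.6 to 1.8 per arm shown above rests on an assumed 1% to 3% rate. The direction of any bias depends on whether abandonment differs by arm, which the protocol does not address. The primary endpoints, analysed by intent-to-treat, are not touched. This should be changed because the wording is cheap to correct.

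**What to change.** 1. In section 9.5, leave AT as it is. Section 9.6.1 appears to plan further primary-endpoint analyses in it (printed there as AS), and widening AT would put subjects without a CI632D in place into the CI632D impedance group.
2. In section 9.5, add a separate safety set: every randomised subject in whom insertion of a CI632D or CI632 was attempted. Name it in 9.7 as the population for the safety analysis.
3. State one grouping rule for that set: any cochlear insertion of a CI632D array counts as CI632D, whatever device is finally left in place.
4. List subjects exposed to more than one array type separately.
5. Align the randomisation-group sentence in 9.7 with this rule.

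**Cost.** The change is to wording only. Surgery, device exposure and adverse events are already recorded, so no new data are needed. A few mixed-exposure subjects will be attributed to CI632D, including events that occur later under a retained CI632, which may make its rate look slightly worse; the separate listing lets a reader see this. Subjects who leave with another implant may be followed for as little as 30 days, so the 6- and 12-month tables should show their shorter observation.
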